3.3.4 Rationale for Single-Blind Placebo Dose

The “placebo effect” is a readily observed phenomenon in clinical trials and specifically in clinical trials involving the testing of a pharmacologically active moiety in asthma (Kemeny et al. 2007; Enck et al. 2008; Dutile et al. 2014). Because of this phenomenon, significant variability has been observed in previous trials in severe asthma. In an effort to minimize the placebo effect, eligible patients will be given one single-blind placebo dose at the run-in visit (Week 0), 2 weeks prior to randomization. Patients will not be eligible for randomization to double-blind treatment if they meet at least one of the following criteria:

- Absolute percentage point change (increase or decrease) of 15 or more in morning pre-bronchodilator percentage of predicted FEV₁ from screening to the randomization visit
- Absolute change (increase or decrease) in FeNO of ≥ 20 ppb and $\geq 40\%$ relative change between screening and randomization visits

Patients will remain on their background asthma medications throughout the screening, run-in, and treatment periods.

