 - Patients are allowed up to three attempts to meet reversibility criteria, within the screening period (see Section 4.5.2 for details).
 - Specific guidelines for performing and interpreting bronchodilator reversibility testing, including medication-withholding strategies and appropriate dosing of short-acting bronchodilators, will be provided to investigators.
- Uncontrolled asthma during the screening period, defined as an ACQ-5 score ≥ 1.5 and at least one of the following symptoms of asthma that is not controlled according to EPR3 (2007) and GINA (2015) guidelines *during each of 2 consecutive weeks*:
 - Nighttime awakening ≥ 1 time/week
 - Use of short-acting rescue therapy > 2 days/week

- Documented history of at least one asthma exacerbation within 12 months prior to screening while on daily ICS maintenance therapy (same or higher dose as at screening), defined as new or increased asthma symptoms (wheezing, coughing, dyspnea, chest tightness, and/or nighttime awakenings due to these symptoms) that result in one or both of the following:
 - Hospitalization or emergency department, urgent care visit, or urgent unscheduled office visit requiring administration of asthma treatment, such as bronchodilators and/or systemic corticosteroids, in addition to baseline controller medications
 - Treatment with systemic corticosteroids for ≥ 3 days or a long-acting depot corticosteroid preparation with a therapeutic effectiveness of ≥ 3 days
- Demonstrated compliance with required use of the eDiary, defined as documenting asthma controller medication use and answering questions related to asthma symptoms, nighttime awakenings due to asthma, and use of short-acting rescue therapy on 5 of 7 days during each of 2 consecutive weeks during the screening period (see Section 4.5.5.2 and Section 4.5.5.3 for details)
- Demonstrated compliance with required PEFr measurements, defined as measuring PEFr on 5 of 7 days during each of 2 consecutive weeks during the screening period (see Section 4.5.5.1 for details)
- Demonstrated adherence with usual asthma controller medication regimen, defined as patients responding affirmatively that they have taken their asthma controller medications on 5 of 7 days during each of 2 consecutive weeks during the screening period, as recorded in the eDiary
- Demonstration of acceptable inhaler, peak flow meter, and spirometry techniques at screening

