The evening diary ([Appendix 4](#)) is comprised of 3 measures.

1. Asthma Daily Symptom Diary: Daytime Symptoms

The ADSD (daytime symptoms) includes 7 items that allow patients to rate the severity of their daytime asthma symptoms since they got up in the morning on an 11-point scale ranging from 0 (none) to 10 (as bad as you can imagine).

A single item is used to assess each of the following concepts:

- Breathing
 - Wheezing
 - Shortness of breath
 - Chest tightness
 - Chest pain
 - Cough
 - Feeling of mucus in the chest
 - The ADSD daytime symptom questions will be asked daily from screening (Visit 1) through Week 54.
2. Short-acting symptom relief medication (short-acting rescue therapy)

Patients will be asked whether they used short acting rescue medication to relieve their asthma symptoms during the day (yes/no). If “yes,” they will be asked whether they used an inhaler and whether they used a nebulizer (“breathing machine”) with instruction to choose “all that apply.” The short-acting symptom relief medication question will be administered every evening beginning at screening through Week 54.

3. Patient Global Impression of Severity

The PGIS completed in the evening diary asks patients to rate their daytime asthma symptoms on an 11-point scale ranging from 0 (no symptoms) to 10 (as bad as you can imagine). The evening diary PGIS will be administered 5 times: at the run-in visit, the randomization visit, one day prior to Week 14 visit, one day prior to Week 26 visit, and one day prior to the Week 54 visit.

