4.2 DEFINITION OF BASELINE

Baseline is defined as the last available pre-treatment value taken on or before the day of randomization (Week 2 visit) for all assessments, with the exception of the following efficacy endpoints: patient-reported use of short-acting rescue therapy, and patient-reported daytime asthma symptom severity as measured by Asthma Daily Symptom Diary (ADSD). For these outcome measures, details for derivation of baseline values can be found in [Section 4.5.2](#).

Baseline measurements will be used for the summary of demographic characteristics, as well as for all change-from-baseline analyses of efficacy, safety, and PD endpoints (including change from baseline in FEV1, CGIC, blood eosinophil count, and FeNO, and improvement from baseline in AQLQ(S), ACQ-5, SGRQ, ACQ-7).

For endpoints that are defined in terms of change from baseline or improvement from baseline, patients who do not have a baseline measurement will be excluded from the analyses.

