Asthma rescue medication use as recorded in the patient's daily electronic diary (e-Diary) will be used for analysis. For each patient, baseline asthma rescue medication use will be defined as the proportion of days with rescue medication use over a 14-day period

prior to the Week 0 visit (i.e. during screening). Patients must have two consecutive compliant weeks during screening in their asthma rescue medication use to have a baseline score calculated. During screening, a patient is compliant in a week if they have at least 5 of 7 days of non-missing entries of asthma rescue medication use. The baseline proportion of days with asthma rescue medication use will first be calculated using the two consecutive screening compliant weeks prior to the run-in visit. However, if the condition of two consecutive screening compliant weeks does not hold in the 14 days prior to the run-in visit, the window will be shifted back by 7 days until a period of two consecutive screening compliant weeks is identified. As one of the inclusion criteria for patients to enter the run-in period is completion of the e-Diary for at least 5 of 7 days during each of 2 consecutive weeks during the screening period, i.e., patients having two consecutive screening compliant weeks, missing baseline score is not expected. In the rare event that a patient does not have a valid baseline score, the patient will be excluded from this analysis.

Although rescue medication is to be recorded each morning and each evening, any day on which at least one entry is collected will be included in analyses. For each patient and monthly post-baseline assessment timepoint (i.e., Week 6, Week 10, ...Week 54), the post-baseline asthma medication use for that timepoint will be defined as the proportion of days with rescue medication use over the 28 days on or prior to the timepoint (inclusive). Patients must have recorded their asthma rescue medication use at least once a day for at least 14 days during a 28-day interval to have a score calculated for the respective timepoint. Missing entries will be excluded from the calculation. For example, if a patient has only recorded rescue medication use for 20 of the 28 days, then the proportion of days will be calculated out of the 20 days with an entry.

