The absolute change from baseline in the proportion of days with asthma rescue medication use will be summarized by treatment arm and timepoint. The absolute difference in mean change in proportion of days of rescue medication use from randomization at Week 54 between each treatment arm and the placebo arm will be estimated on the basis of an MMRM analysis. The model will use absolute change from baseline as the response variable and include terms for treatment arm, study visit, treatment arm by study visit interaction, baseline asthma rescue medication use (as a continuous variable) as well as its interaction with study visit, and the baseline covariates described in Section 4.5. Study visit will be included as a categorical variable. An unstructured covariance matrix will be specified to model the within-subject errors. Point estimates, 95% CIs, and p-values for the treatment difference (MSTT1041A vs. placebo) will be calculated for each MSTT1041A dose level based on the model for all study visits including Week 54.

Asthma-Related Nighttime Awakenings

Nighttime awakenings, as recorded each morning in the patient's daily e-Diary, will be used for analysis. For each patient, the proportion of weeks without a nighttime

awakening from baseline through Week 54 will be calculated. The randomization visit (Week 2) will be used as baseline.

From the randomization visit, the subsequent weeks will be counted by a 7-day window until Week 54 is reached. For each 1-week period after randomization visit, if there are 4 or more morning diaries with missing entries, the 1-week period is considered a non-compliant week and the corresponding value will be considered as missing. These missing values will not be imputed, and these missing weeks will not be included in the denominator when calculating the proportion of weeks. However, if there are >3 morning diaries with missing entries during a 1-week period but one of the available entries for the 1-week period reports a nighttime awakening, this 1-week period will be included in the calculation.

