The proportion of weeks without a nighttime awakening due to asthma will be summarized by treatment arm. The absolute difference in mean proportion between each MSTT1041A dose level and the placebo arm will be estimated on the basis of an analysis of variance model. The model will use the proportion of weeks without a nighttime awakening due to asthma as the response variable and include terms for treatment arm and the baseline covariates described in Section 4.5. Point estimates, 95% CIs, and p-values for the treatment difference (MSTT1041A vs. placebo) will be calculated for each MSTT1041A dose level.

Daytime Asthma Symptom Severity

Daytime asthma symptom severity will be assessed by patient ratings of asthma symptoms each evening, as recorded in the ADSD on their e-Diary.

The daily daytime symptom scores are calculated each day as an average of the six core evening diary symptoms: difficulty breathing, wheezing, shortness of breath, chest tightness, chest pain and cough. Each question is scored from the scale of 0 to 10, in which higher scores indicate worse symptoms. The daytime symptom score for each timepoint is then calculated as a weekly average of the 7 individual average daily scores. Daily scores will only be calculated if data for 4 or more items per day are available.

Daily scores will be averaged over the previous week prior to each scheduled visit (i.e., 7 days prior to Week 54 visit). For each week after randomization visit, if there are >3 days with missing scores out of the 7 days, the week is considered a non-compliant week and the average score for the week will be considered as missing. These missing values will not be imputed but will be handled directly by the MMRM model.

The baseline value will be derived based on a 2-week screening period prior to the Week 0 visit. Patients must have two consecutive compliant weeks during screening to have a baseline score calculated. During screening, a patient is compliant in a week if they have at least 5 of 7 days of non-missing scores. The baseline score will first be calculated using the two consecutive screening compliant weeks prior to the run-in visit.

However, if the condition of two consecutive screening compliant weeks does not hold in the 14 days prior to the run-in visit, the window will be shifted back by 7 days until a period of two consecutive screening compliant weeks is identified. Patients without a 'valid' baseline score will be excluded from the analysis.

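### The rescue-use and ADSD models take baseline from screening only and leave out the run-in diary: the contrast with placebo is unbiased, but by-arm changes carry regression to the mean and some precision is lost

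*SAP*

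**What the plan says.** SAP 4.2 sets the general rule: "Baseline is defined as the last available pre-treatment value taken on or before the day of randomization (Week 2 visit) for all assessments". It then names two exceptions, rescue use and ADSD daytime severity.

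SAP 4.5.2 defines both exceptions. Rescue-use baseline is the proportion of days with use over 14 days "prior to the Week 0 visit (i.e. during screening"). For ADSD, "The baseline value will be derived based on a 2-week screening period prior to the Week 0 visit". Each screening week needs at least 5 of 7 diary days. If the last 14 days do not qualify, the window moves back by 7 days until two compliant weeks are found.

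Other secondary endpoints are anchored later. FEV1 follows the general rule, AQLQ(S) and ACQ-5 use the Week 2 value, and nighttime awakenings are counted from randomization.

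Protocol 3.3.4 places the placebo dose after the screening window, with the aim of reducing the placebo effect: "eligible patients will be given one single-blind placebo dose at the run-in visit (Week 0), 2 weeks prior to randomization". Protocol 4.1.1.1 defines uncontrolled asthma in screening as ACQ-5 of at least 1.5 plus either nighttime awakening or "Use of short-acting rescue therapy > 2 days/week", in each of 2 consecutive weeks.

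Protocol 4.5.5.3 has the rescue-use questions asked every morning and evening from screening through Week 54. On ADSD it says: "The ADSD daytime symptom questions will be asked daily from screening (Visit 1) through Week 54".

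Both endpoints are analysed by an MMRM of change from baseline, with that baseline and its visit interaction as covariates. For rescue use, however, SAP 4.5.2 describes the contrast as "The absolute difference in mean change in proportion of days of rescue medication use from randomization at Week 54".

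**The concern.** Three features of the screening window raise the question.

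- It closes before the placebo dose, so any response to that dose counts as change from baseline.
- It lies in the period when patients had to show poor control. Those who qualified on rescue use were picked partly for high values in those weeks, and such values tend to fall later without treatment.
- A measurement closer to randomization is collected every day and enters neither model.

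ADSD is fourth and rescue use sixth among the secondary endpoints in the fixed sequence (SAP 4.5, Table 1), and the SAP summarizes change from baseline by arm for both. At stake are how those by-arm changes are read and how precise the Week 54 contrasts are.

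**Working it through.** **Step 1. Timing.** The run-in visit is 2 weeks ±5 days before randomization (Protocol Appendix 1, footnote b), so the run-in lasts 14 − 5 = 9 to 14 + 5 = 19 days. The baseline window ends before it, hence at least about 9 days before the first double-blind dose, and earlier if shifted back.

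**Step 2. Strength of selection.** More than 2 days a week means at least 3/7 = 42.9% of days in each qualifying week. This floor applies only to patients who qualify on rescue use; the awakening route has none. Screening may last 12 to 28 days (Protocol 4.5.2), so the qualifying and baseline weeks coincide when screening is short but can differ when it is long. ADSD is not an entry criterion. It is affected only through its correlation with ACQ-5, awakenings and rescue use.

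**Step 3. The contrast.** Let B be baseline and Y the Week 54 value. The difference in mean change is (Y_active − Y_placebo) − (B_active − B_placebo). B is fixed before randomization, so the second bracket has expectation zero whatever window defines B. Regression to the mean and run-in response are the same in all arms and cancel.

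**Step 4. Size for rescue use.** The documents give no mean, SD or correlation for either endpoint, so there is no figure in the plan to reproduce and every parameter below is an assumption. Daily use was simulated as Bernoulli on the logit scale with a person effect and a weekly autoregressive effect. Eligibility was at least 3 of 7 days in both screening weeks, or the awakening route with the stated probability. The endpoint was the last 28 days before Week 54. There was no true change or placebo response in the placebo arm. The run-in was set at 14 days, and each scenario had 400,000 candidates.

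| Person SD, weekly SD, weekly correlation, mean logit, awakening route | Placebo change from screening (points) | From run-in (points) | Gap | r with Week 54: screening | r: screening and run-in pooled | Variance reduction |
|---|---|---|---|---|---|---|
| 1.5, 1.0, 0.80, 0, 0% | −10.4 | −5.3 | 5.1 | 0.424 | 0.492 | 7.6% |
| 1.5, 1.0, 0.80, 0, 50% | −3.6 | −1.9 | 1.7 | 0.629 | 0.666 | 7.9% |
| 1.5, 1.0, 0.80, −1, 0% | −15.1 | −7.6 | 7.5 | 0.396 | 0.469 | 7.5% |
| 2.0, 1.0, 0.80, 0, 30% | −4.6 | −2.3 | 2.3 | 0.705 | 0.740 | 10.1% |
| 1.0, 1.5, 0.80, −0.5, 30% | −10.9 | −6.2 | 4.7 | 0.285 | 0.313 | 1.8% |
| 1.5, 1.0, 0.95, 0, 30% | −5.7 | −3.8 | 1.9 | 0.592 | 0.621 | 5.4% |

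Variance reduction is 1 − (1 − r²_pooled)/(1 − r²_screening). First row: 1 − (1 − 0.492²)/(1 − 0.424²) = 1 − 0.7579/0.8202 = 7.6%. Entering the two means as separate covariates can fit only as well or better.

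**Step 5. Contrast and simple replacement.** With an active effect of −0.5 on the logit scale, the adjusted difference was −0.0836 with the screening baseline and −0.0838 with the run-in baseline (first row), and −0.0812 and −0.0809 (second row). These differences are within simulation error. Replacing screening by run-in changed the variance of the estimate by only 0.1% to 3%, so the standard error by at most √1.03 − 1 = 1.5%.

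**Step 6. Other assumptions.** A second simulation, with every patient qualifying on rescue use and a correlation of 0.5 between adjacent periods, gave 7 to 13% lower residual variance with both covariates. Over a wider set of assumed parameters the range is about 2 to 20% for variance and about 1 to 8 points for the gap. In standard error, 2 to 20% is 1 − √0.98 = 1% to 1 − √0.80 = 11%.

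**The case against.** The screening baseline is a deliberate choice. SAP 4.2 names the two exceptions, and SAP 4.5.2 notes that a missing rescue-use baseline is not expected because screening diary compliance was an entry requirement. No such requirement covers the run-in. This stands, and it is why the screening baseline should stay.

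The run-in is not an unselected period either. Randomization requires FEV1 within 40 to 80% of predicted at Week 2, no large FEV1 or FeNO change since screening, and no systemic corticosteroids during the run-in (Protocol 4.1.1.2, 4.1.2.2, 4.4.3). Excluding variable patients also shapes the randomized population for every endpoint, including these two. A fixed 14-day window before randomization would reach back into screening whenever the run-in is shorter than 14 days. These points stand too, and they make outright replacement a trade-off.

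A reader might infer that the treatment effects are inflated, or that the place of these endpoints in the alpha-controlled sequence puts type I error at risk. The documents do not support that: every test compares an arm with placebo, and randomization follows both selection and baseline. Nor does the SAP generally present these changes as starting at randomization. That wording appears once, in the rescue-use contrast sentence; the model response, the by-arm summaries and all the ADSD text say baseline.

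None of this explains why the run-in diary should be left out of the models, or why the by-arm changes carry no caveat.

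**Conclusion.** The point holds in a limited form. The screening baselines are valid for testing. The by-arm changes overstate improvement after randomization, because they include regression to the mean and any run-in placebo response. For rescue use the excess over a run-in baseline is about 1 to 8 percentage points of days under assumed parameters, and it is smaller when many patients qualify on awakenings. Part of the regression to the mean remains even with a run-in baseline. No figure is available for ADSD; the direction is likely the same, through correlation only.

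Both MMRMs also omit a pre-randomization measurement already in hand. Adding it would lower residual variance for rescue use by about 2 to 20%, mainly because more baseline days are used rather than because they are closer to randomization. The documents give no correlations with which to fix the figure. The mismatch between the rescue-use contrast sentence and its baseline definition is certain and needs no assumption.

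A reader might conclude that the screening baseline materially weakens the adjustment and should be replaced. Replacement alone gained only 0.1 to 3% of variance in the six scenarios, so that is not supported.

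**What to change.** Before the Week 54 analysis, since SAP Section 1 bars changes at or after it:

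1. Keep the screening baseline. In both MMRMs (SAP 4.5.2), add a second covariate with its visit interaction: the mean of all non-missing run-in diary days from Week 0 to the day before randomization, whatever the run-in length. State a minimum number of days, for example half of the run-in days, in line with the existing 14-of-28-day rule for rescue use. Also state a rule for patients below that minimum, for example prediction from the screening value pooled over arms, without using treatment or post-randomization data.
2. In the rescue-use contrast sentence of SAP 4.5.2, replace *from randomization* with *from baseline (screening)*.
3. Report by-arm change from the run-in mean as a supplementary summary for both endpoints. Note beside the main summaries that change from the screening baseline includes regression to the mean and run-in response.

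The cost is SAP wording and programming, with no new data. The model gains one slope per visit: for rescue use, monthly from Week 6 to Week 54, (54 − 6)/4 + 1 = 13 parameters. Some patients will have incomplete run-in diaries and fall under the stated rule.

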Appendix 4 Daily Diary (cont.)

MORNING DIARY QUESTIONS

Nighttime Awakening Due To Asthma

[Administered every morning from screening through Week 54]

Did any of your asthma symptoms wake you up since you went to bed last night?

- Yes
 No

Short-Acting Symptom Relief Medication

[Administered every morning from screening through Week 54]

After going to sleep last night, did you take any rescue medication for your asthma symptoms (shortness of breath, cough, wheeze, or chest tightness)?

- No, I did not take any rescue medication
 Yes, I used a rescue inhaler
 Yes, I used a nebulizer (breathing machine)

Patient Global Impression of Severity (PGIS)

[Administered at 4 time points: Run-in Visit; Randomization Visit; one day prior to Week 26; one day prior to Week 54]

Overall, please rate your asthma symptoms since you went to bed last night.

0	1	2	3	4	5	6	7	8	9	10
No Symptoms										As bad as you can imagine

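### Nighttime awakenings (SAP 4.5.2): a sparsely filled diary week counts only if it contains an awakening; keep the rule, but add a baseline awakening covariate and a night-level supportive analysis

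*SAP*

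**What the plan says.** The endpoint is fifth of the seven secondary endpoints in the fixed testing sequence (SAP 4.5, Table 1). For each patient the SAP computes "the proportion of weeks without a nighttime" awakening from randomization to Week 54. Weeks are formed so that "the subsequent weeks will be counted by a 7-day window until Week 54 is reached", which makes 52 windows. The diary asks one yes/no question, "Administered every morning from screening through Week 54" (Protocol Appendix 4), so a full week has seven entries.

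SAP 4.5.2 then gives three rules:

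- Compliance: "if there are 4 or more morning diaries with missing entries, the 1-week period is considered a non-compliant week" and its value is missing.
- Default: there is no imputation, and "these missing weeks will not be included in the denominator when calculating the proportion of weeks".
- Exception, worded for weeks in which more than three mornings are missing: provided that "one of the available entries for the 1-week period reports a nighttime awakening, this 1-week period will be included in the calculation". I read this as at least one entry.

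Four or more missing and more than three missing are the same set of weeks. The treatment difference "will be estimated on the basis of an analysis of variance model", with terms for arm and the Section 4.5 covariates (eosinophils, exacerbation history, ICS dose, region). No weighting, minimum number of evaluable weeks or baseline awakening term is specified. Section 4.8 only refers back to 4.5.2.

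**The concern.** A recorded awakening settles the status of its own week, so keeping that week looks harmless. The difficulty lies in the proportion. Sparse weeks that are restored are all failures, and a sparse week with only clear entries has no way back in. The score therefore depends on how often the patient fills in the diary as well as on how often the patient wakes. A 0% built on one restored week also carries the same weight in the analysis of variance as a score built on 52 observed weeks.

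At stake is the arm comparison on a type I error-controlled secondary endpoint. If diary completion differs between arms, part of the estimated difference reflects completion. The tipping-point analyses in SAP 4.5.4 would not necessarily show this. They are run only for endpoints found significant, and the method described for continuous secondary endpoints concerns change from baseline to Week 54, which this proportion is not.

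**Working it through.** The plan gives no expected proportion, standard deviation or completion rate for this endpoint, so there is no figure to reproduce. The 7-day week, the threshold of four missing mornings and the 52 windows come from SAP 4.5.2. The nightly awakening probability p and the chance q that a morning is recorded are my assumptions, with independent nights and entries missing completely at random.

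**Step 1: values a week can take.** Enumerating all 3^7 = 2,187 weekly patterns (missing, no awakening, awakening):

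- 0 entries: missing only
- 1, 2 or 3 entries: failure or missing
- 4 to 7 entries: failure or awakening-free

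**Step 2: a patient with three entries in every week.** There are 3 × 52 = 156 entries. One reported awakening gives 0/1 = 0%, and the 51 clear weeks are dropped. The chance of scoring 0% is 1 − (1 − p)^156, otherwise the patient is missing:

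- p = 0.01: 0.79 (true awakening-free proportion 0.99^7 = 0.932)
- p = 0.02: 0.96 (true 0.98^7 = 0.868)
- p = 0.05: above 0.999 (true 0.95^7 = 0.698)

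**Step 3: random completion.** With M ~ Binomial(7, q) recorded mornings:

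- A = P(M ≥ 4, none awake)
- B = P(M ≥ 4)
- C = P(M ≤ 3, at least one awake)
- SAP score = A / (B + C); score with the exception deleted = A / B

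For q = 0.50 and p = 0.05: A = 0.395, B = 0.500, C = 0.058. The SAP score is 0.395 / 0.558 = 0.709, and the deleted version is 0.395 / 0.500 = 0.791.

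All rows at p = 0.05, true value 0.698:

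| Completion | SAP rule | Exception deleted |
|---|---|---|
| 90% | 0.724 | 0.724 |
| 70% | 0.752 | 0.766 |
| 60% | 0.743 | 0.780 |
| 50% | 0.709 | 0.791 |
| 40% | 0.637 | 0.798 |
| 30% | 0.502 | 0.804 |
| 20% | 0.284 | 0.808 |

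Two errors pull in opposite directions. A compliant week with four to six entries is scored clear if the awakening fell on an unrecorded night, which overstates. The exception understates. They roughly cancel near 50% completion. At 60-90% the SAP rule overstates by 2.6 to 5.4 points here (0.6 to 1.3 points at p = 0.01), and it understates clearly only below about 45%.

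**Step 4: effect on the arm comparison.** Suppose 15% of one arm and 5% of the other complete 20-30% of mornings, and everyone else completes 90%. The spurious difference is (0.15 − 0.05) × (score at low completion − score at 90%). At p = 0.05:

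- SAP rule: 0.10 × (0.284 − 0.724) = −4.4 points at 20%, and 0.10 × (0.502 − 0.724) = −2.2 points at 30%. The arm with poorer completion looks worse.
- Exception deleted: 0.10 × (0.808 − 0.724) = +0.8 points at 20%, and 0.10 × (0.804 − 0.724) = +0.8 points at 30%. That arm looks better.

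For p from 0.02 to 0.20 the ranges are −1.3 to −4.4 points under the SAP rule and +0.4 to +1.5 points after deletion. If the poor completers are instead at 50%, the SAP rule gives −0.15 points and deletion +0.67 (p = 0.05).

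**Step 5: a night-level score.** Nights without an awakening over nights recorded has expectation 1 − p at every q, so under the same assumptions the Step 4 difference is zero.

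**The case against.** The strongest defence is that the exception corrects a real optimism. Partly filled compliant weeks are scored too favourably, and retaining known failures offsets this. The table bears that out: at 40% completion and above, deleting the exception is never closer to the truth. That part stands, and it is why deletion should not be the remedy.

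The low-completion region is also not something the documents predict. Entry required diary completion on 5 of 7 days in each of two consecutive weeks (Protocol 4.1.1.1), the device issues reminders (4.5.5.3), and sites review compliance and retrain (4.5.5). Patients who stop study drug are asked to continue all assessments (4.6.2). One who abandons the diary altogether has zero entries and is missing under either rule. The patient with exactly three entries in all 52 weeks is a boundary case, and p = 0.02 means only about one awakening in seven weeks.

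What this leaves unanswered is the dependence on completion itself. An offset that varies with completion cannot protect a comparison when completion differs by arm, and entry requirements do not guarantee a year of entries. The pattern of missingness matters too. For a patient with 26 full weeks and 26 three-entry weeks at p = 0.05, the SAP rule gives about 0.698 / (1 + 0.143) = 0.611, where dropping all sparse weeks gives the true 0.698.

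A reader might infer that the rule biases the endpoint downward or disadvantages one arm. The documents support neither: they report no completion rates, overall or by arm, and the sign changes with completion.

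**Conclusion.** The defect in the rule follows from the wording and needs no assumption: inclusion of a sparse week depends on its outcome, and a patient who is sparse in every week can score only 0% or missing. A patient with some compliant weeks is not forced to 0%.

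The size is conditional on independent nights, random missingness and assumed rates. At p = 0.05 the error is about +1 point at 50% completion, +3 to +5 at 60-90%, −6 at 40%, −20 at 30% and −41 at 20%. The large errors need completion that nothing in the documents suggests. No net direction of bias, and no actual distortion of the arm comparison, can be claimed.

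It is tempting to conclude that the exception should simply be removed. The figures do not support that. Removal leaves an overstatement of about 3 to 11 points at p = 0.05 and reverses the spurious arm difference, so that poorer completion is rewarded.

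A separate gap is plain. The models for FEV1, AQLQ(S), rescue use and daytime symptoms include the patient's baseline value, and ACQ-5 follows the AQLQ(S) method. The awakening model has no such term, although awakenings are recorded every morning from screening.

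**What to change.** Keep the main scoring rule and make two additions to SAP 4.5.2:

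1. Add the patient's screening awakening frequency as a covariate in the analysis of variance. It could be taken from the two compliant screening weeks that the SAP already uses for the rescue-medication baseline. This should improve precision and adjusts for chance imbalance. It does not remove the dependence on the outcome.
2. Add a supportive night-level analysis: nights without an awakening over nights recorded, weighted by nights recorded or fitted as a binomial model with over-dispersion, with the same covariates. It keeps every recorded awakening, does not depend on completion when entries are missing at random, and its denominators show diary completion by arm.

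The cost is SAP wording and one extra model; no new data are needed. The night-level result describes nights, not weeks, so it supports the main analysis and does not replace it. It would not be protected if patients skip the diary because of a bad night. Section 1 of the SAP allows no changes at or after the 54-week analysis, so both additions must be made before then.
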